### 9.1. Analysis Conventions

The following conventions will be applied to all data presentations and analyses.

- Tables and listings will be presented in landscape orientation.
- Tables will be presented for analysis populations as defined in the title of the tables.
- Listings will be presented for the enrolled population.
- All the displays will be in Tahoma 8pt font.
- All tables and listings will have footer sections which will contain the name of the program.
- For all tables and listings, the titles will appear in the body of the document. The title will include the sponsor name, protocol name, date and time of generation, version (Draft/Final), page number in the format Page X of Y, Table/Listing number and name.

An example is given below

Ion Channel Innovations, LLC		Draft -DDMMYYYY:HH:MM
Protocol: ION04ED		Page x of y
Table XX.X.X		
Table Title		
Population		

- Summary tables will contain footnotes in the body of the title that reference any data listings or tables associated with the table or figure (e.g. Reference: Listing 16.X.XX).
- Additional footnotes may be added as per the STL shells.
- The outputs have to be created as per the shells that will be provided along with this analysis plan.
- Guidelines provided in the STL shells under "Programming notes" should be referred to by the programmers for clarity on shells.
- All means and medians will be formatted to one more decimal place than the measured value. Confidence intervals and standard deviation values will be formatted to two more decimal places than the measured value. Minimum and maximum values will be presented with the same number of decimal places as the measured value.
- The number and percentage of responses will be presented in the form XX (XX %) where the percentage as whole numbers will be in parentheses.

**ION04ED**

- All p-values will be presented with at least 3 decimal places ensuring meaningful representation.
- All summary tables will include the total number of subjects in the population that is being analyzed based on treatment randomized and received study drug. This information will be given in the column headings in each table.
- All listings will be ordered by treatment cohort, subject number and visit date (if applicable).
- Date variables will be formatted as DDMMYYYY for presentation.
- SAS® Version 9.2 will be used for all data analysis.
- MedDRA version 19.1 and WHO version released on DEC 01, 2017 will be used for coding adverse events and concomitant medications, respectively.

## **9.2. Descriptive Methods**

The study comprises of two cohorts comprising of three treatment groups namely

- **Cohort 1:** *h*Maxi-K- comprising of two treatment groups; *h*Maxi-K 8000 $\mu$ g and *h*Maxi-K 16000 $\mu$ g
- **Cohort 2:** Placebo- which was administration of PBS-20% sucrose

All outputs will be presented with respect to the above two cohorts and overall. Cohort 1 will be further sub-categorized with respect to the two treatments.

The various baseline and demographic characteristics will be analyzed for the randomized population. For quantitative variables, the following descriptive statistics will be computed: number of subjects (n), number of missing values/subjects, mean, standard deviation, minimum, maximum, median, Q1 and Q3. For qualitative variables, the frequency and percentage of subjects and/or events will be calculated. All listings will include the subject identifiers, the treatment group/cohort that the subject is randomized to and the tables will be presented by the treatment cohorts to which subjects are randomized. The characteristics that will be analyzed are as follows

### **Demography**

At screening, demographic data including: date of birth, age, race, height and weight. The date of birth, age, height, weight and BMI will be listed in the demography listing. In addition to this, the information pertaining to subject being diabetic, informed consent and the analysis population flag will be presented.

In addition, descriptive statistics for relevant variables will be presented in tabular format. The age and BMI will be calculated as mentioned in [section 6](#) of this document. Age, height, weight and BMI will be summarized by number of subjects (n), number of missing values/subjects, mean, standard deviation, minimum, maximum, median, Q1 and Q3. Categorical parameters namely race and subject being diabetic will be summarized using counts and percentages. The percentages will be calculated based on the number of non-missing values.

### **Medical History**

Medical History terms will be coded using MedDRA version 19.1. A listing will be created to present the medical history information collected in the CRF. A table will be created to present the count and percentage of subjects with medical conditions falling under each body system and preferred term within each body system.

**ION04ED** **Physical examination**

A complete review of body systems will be performed at all visits as part of physical examination. The number and percentage of subjects having normal, abnormal or not done responses against each body system at screening and post-dose visits 1-7 (week -2 - 24) will be tabulated. The corresponding listing will present the body system, responses and details of abnormalities (if applicable).

 **Physical Examination of Penis**

Physical examination of the penis will be done at all visits and will include inspection, palpation and neurosensory testing. The percentage of subjects having normal, abnormal or not done responses against each parameter will be tabulated. The corresponding listing will present the parameter, responses and details of abnormalities (if applicable).

 **Electrocardiograms**

A 12-lead ECG will be performed at screening and post-dose visits 1-7 (week -2 - 24). The descriptive statistics for the following parameters will be presented: heart rate, PR interval, QT interval, QTc, QRS duration, QRS axis, QTcF, QTcB and RR duration. The number and percentage of subjects under each categorization of rhythm and overall evaluation will be further presented. The corresponding listing will include the results against above parameters, significance, details of clinically significant results and differences from previous assessment. Both the ECG overreader's reading and site readings will be evaluated. Shift tables will also be presented for the relevant parameters.

 **Vital Signs**

Vital signs will be collected at all visits. Vital signs will include

- Brachial blood pressure (BP)
- Pulse rate
- Oral temperature
- Weight

Descriptive statistics will be presented for all the above parameters at all the time points of collection with respect to the treatment cohorts. The corresponding listing will present the results.

 **Prior and Concomitant Medication**

Prior and concomitant medications will be listed and tabulated. Listings will present the information collected against these terms and a flag to identify prior and concomitant medications. Separate tables will be generated to present the counts and percentages of subjects with prior and concomitant medications falling in each therapeutic class and chemical subgroup (obtained as part of WHODD coding).

 **Inclusion/Exclusion criteria**

The information pertaining to the inclusion and exclusion criteria will be listed.

 **Compliance to study medication**

The subjects are planned to be assigned to one of the below treatment cohorts

- **Cohort 1:** *h*Maxi-K- comprising of two treatment groups; *h*Maxi-K 8000 $\mu$ g and *h*Maxi-K 16000 $\mu$ g
- **Cohort 2:** Placebo- which was administration of PBS-20% sucrose

## STATISTICAL ANALYSIS PLAN

---

### ION04ED

Compliance to study medication will be summarized and listed. The summary table will include the number and percentage of subjects randomized to the two treatment cohorts. Further categorization on the treatments administered within each cohort will be provided. It will also include the number and percentage of subjects who were administered treatment. The listing will include the details pertaining to treatment cohort, treatment, randomization number, date of administration and whether treatment was administered.

#### **Randomization**

The data pertaining to the treatment to which subject has been randomization will be listed.

#### **Protocol Deviations**

List of protocol deviations will be provided by the CRO and this will be classified into minor or major based on inputs from the sponsor. The subjects reporting protocol deviations will be listed along with the deviation and its classification.

#### **Study Termination**

The study completion listing will be developed based on the data obtained in the study termination form. The listing will include the date of completion/withdrawal, status at the end of study, main reason for not completing, date of last contact and date of death (if applicable). All patients who prematurely discontinued during the study will be listed by discontinuation reason for the randomized ITT Population.

#### **Subject Disposition**

A table representing the counts and percentages of subjects attaining the various study milestones namely enrolment, randomization, meeting analysis population criteria, protocol deviations and study completion or withdrawal will be presented. The reason for discontinuation will also be summarized within the table.

#### **Efficacy endpoints**

The International Index of Erectile Function (IIEF) is a validated, self-administered questionnaire that has been shown to be a cross-culturally and psychometrically valid measure of male erectile dysfunction.

The test contains 15 questions in five domains:

- a) erectile duration/function (six items)
- b) orgasmic function (two items)
- c) sexual desire (two items)
- d) intercourse satisfaction (three items)
- e) overall sexual satisfaction (two items)

The summary tables against the data collected through the IIEF will include the descriptive statistics against the total and domain specific score by visit. The domain specific scores will be the sum of the scores against questions under the respective domain. The total score will be the sum of scores of all the questions. The listings will also be presented against all the data that is collected.

SEP is a diary in which subjects record each sexual attempt made throughout the study and is composed of 5 questions assessing sexual function. SEP 2 evaluates the penetrability of the erection and SEP 3 the maintenance of the erection.

The summary tables against SEP will include the number and percentages of subjects reporting yes/no against each of the questions. Corresponding listing will also be presented.

**ION04ED**

In addition to the summary tables, tables will be presented against the analysis mentioned in the below section.

### 9.3. Primary Analysis

The primary outcome measures that will be considered to evaluate change in erectile status from baseline following administration of *hMaxi-K* are

- Erectile Function (EF) domain of the International Index of Erectile Function (IIEF)
- Sexual Encounter Profile (SEP): Questions 2 and 3

#### **Erectile Function (EF) domain of the International Index of Erectile Function (IIEF)**

The erectile function domain, questions 1-5, and 15 of the IIEF has been validated to assess erectile changes only. The IIEF EF domain has a 30-point total score, where higher scores reflect better erectile function. The EF domain of the IIEF will be completed at Visit 1 (screening) and V2-V7 (week 0-24).

The total score for a subject for the EF domain will be computed as the sum of the six questions. Descriptive statistics of the domain score will be presented with respect to the subjects receiving *hMaxi-K* (16,000 µg) and placebo at all visits. The change in scores from baseline at each visit will be evaluated using one-sided paired t-test at 5% significance level to assess improvement in scores post treatment when compared to baseline for the two treatment groups separately. Further, a one-sided two sample t-test will be applied to compare the changes from baseline in scores between the two treatment groups. The scores for the other 4 domains on the IIEF will also be computed and analyzed as secondary analyses.

Repeated measures ANOVA will be performed to assess the effect of visit on the total score for each treatment groups. Further a two-sample t test, will be performed to study the effect of treatment groups and time points on the domain scores.

The above analysis will be repeated for comparison between the two treatment cohorts and between *hMaxi-K* 8000µg and placebo treatment groups.

Analysis will be performed including all subjects and the final 15 subjects separately.

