Study Procedures	Following screening and study drug administration at week 0, eligible participants will be evaluated at weeks 1, 4, 8, 12, and 24. At each study visit, participants will have a physical examination including examination of the penis (all visits), vital signs, electrocardiogram (ECG) (all visits). Laboratory evaluations including chemistry and hematology will be done at V1, 3, 4, 6, and 7. Urinalysis will be done V1, 2 (prior to dosing), 3, 4, 6, and 7. Endocrine parameters and PTT, PT, sed rate and CRP will be evaluated at Visit 1, 3 and 7. The participant will complete the erectile function domain of the IIEF and Sexual Encounter Profile (SEP) at screening/baseline and at V2, (SEP and IIEF at V2 prior to dosing) V3, V4, V5, V6, and V7. In all participants, plasma specimens will be collected to assay for the presence of hSlo DNA by PCR (V2-V7). These will be kept frozen at -20°C or less at the site for eventual assay by Sponsor.
Primary Study Outcomes	The primary outcome measures will include the Erectile Function (EF) domain of the International Index of Erectile Function (IIEF), Sexual Encounter Profile (SEP), Questions 2 and 3 from SEP. The IIEF EF domain has a 30-point total score, where higher scores reflect better erectile function. SEP is a diary in which participants record each sexual attempt made throughout the study. The two questions from the Sexual Encounter Profile (SEP) deal with the ability to achieve vaginal penetration (SEP2), and the ability to maintain an erection long enough for successful intercourse (SEP3). The erectile function domain category of the IIEF will be used to evaluate the change in erectile status from baseline following

**Secondary
Study
Outcome****Study Duration****Study Start****Sample Size****Statistical
Analysis**

administration of *h*Maxi-K. Change from baseline on the six questions of the IIEF's Erectile function domain category at every visit after administration of study drug will be calculated and compared among the two dose and one placebo groups.

Safety will be assessed by analysis of adverse experiences, and abnormal findings on clinical laboratory tests, electrocardiogram, and physical examinations.

6 months per participant (approximately 1 year to enroll all participants)

TBD

35 participants; N=11 on 8000 µg; N= 11 on 16000 µg; N= 13 on placebo

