7.3 Visit 3 (Study Week 1)

The following tests and evaluations will be performed:

- Adverse events and concomitant medications since the last visit;
- Physical examination including examination of penis;
- Vital signs (BP, heart rate);
- Electrocardiogram;
- Obtain plasma for the following laboratory determinations:
 - Hematology: Complete Blood Count (CBC) with differential, platelet count, Partial Thromboplastin (PTT), Prothrombin time (PT), sedimentation rate, C-reactive protein;
 - Chemistry: Blood Urea Nitrogen (BUN), creatinine, electrolytes (Na⁺, K⁺, Mg⁺⁺, Ca⁺⁺, CO₂, Cl), albumin, alkaline phosphatase, LDH, GGT, ALT, AST, total bilirubin, total protein, glucose;
 - Endocrine: total testosterone, random cortisol, TSH, T4;

- Urine analysis: microscopic RBC and WBC, protein, glucose, nitrites and specific gravity;
- Plasma specimens will be collected to assay for the presence of *hSlo* DNA by PCR. These will be kept frozen at -20°C or less at the site for eventual assay by Sponsor.
- Participant completes the IIEF and SEP.
- Schedule next study visit.

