10.3.2 Efficacy

The sample size has been estimated assuming a standard deviation of 2.5 and a two sample t-test to have 80% power.

Table 2. Statistical Power

Power	N1	N2	Placebo	Ratio	Alpha'	Mean ₁	Mean ₂	SD ₁	SD ₂
80%	11	11	13	1.111	0.0167	10.0	6.6	2.5	2.5

The mean change in IIEF and SEP and participant questionnaire (unmedicated and active phase) questions will be evaluated at all visits and changes compared to baseline and placebo.

Alpha' is the alpha level adjusted for three multiple comparisons (the two doses compared with each other, and each dose compared with the placebo). Given the three comparisons that incorporated a Bonferroni multiple comparison procedure, the overall alpha level is preserved at .05.

A 10% attrition rate over the 24 weeks of followup is anticipated, which inflates the sample size to approximately 40 subjects in total.

Descriptive statistics will be presented as means and standard deviations for normally distributed data at each timepoint by group, and medians and ranges otherwise. Incidence of adverse events will be presented as relative frequencies. All estimates of differences will be presented with 95% confidence limits. The mean change in IIEF and SEP and participant questionnaire (unmedicated and active phase) questions will be evaluated at all visits and changes compared to baseline and placebo using either paired t-tests for normally distributed changes, or Wilcoxon Sign Rank tests, otherwise. A mixed effects or marginal model will be used to assess trends in changes over time among treatment groups. With regard to missing data, the assumption of missing at random will be assessed by looking for patterns over time, and by comparing those with missing values to all

other subjects with regard to baseline characteristics. Chi-square or Exact tests will be used to compare incidence rates among the treatment groups. All tests of significance with regard to efficacy will be one-tailed, and performed at an overall alpha level of .05 using SAS Version 9.3 or higher, Cary, NC.

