Appendix D. International Index Erectile Function

INTERNATIONAL INDEX OF ERECTILE FUNCTION PAGE 1 OF 2

PARTICIPANT

(check the appropriate box – *In the last month.....*)

1. How often were you able to get an erection during sexual activity?	4. During sexual intercourse, how often were you able to maintain your erection after you had penetrated (entered) your partner?
0. No sexual activity..... 	0. Did not attempt intercourse..... 
1. Almost never / never..... 	1. Almost never / never..... 
2. A few times (much less than half the time)..... 	2. A few times (much less than half the time)..... 
3. Sometimes (about half the time)..... 	3. Sometimes (about half the time)..... 
4. Most times (much more than half the time)..... 	4. Most times (much more than half the time)..... 
5. Almost always/always..... 	5. Almost always/always..... 
2. When you had erections with sexual simulation, how often were your erections hard enough for penetration?	5. During sexual intercourse, how difficult was it to maintain your erection to completion of intercourse?
0. No sexual activity..... 	0. Did not attempt intercourse..... 
1. Almost never / never..... 	1. Extremely difficult..... 
2. A few times (much less than half the time)..... 	2. Very difficult..... 
3. Sometimes (about half the time)..... 	3. Difficult..... 
4. Most times (much more than half the time)..... 	4. Slightly difficult..... 
5. Almost always/always..... 	5. Not difficult..... 
3. When you attempted sexual intercourse, how often were you able to penetrate (enter) your partner?	6. How many times have you attempted sexual intercourse?
0. No sexual activity..... 	0. No attempts..... 
1. Almost never / never..... 	1. One to two times..... 

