
8. How much have you enjoyed sexual intercourse?
 
0. No intercourse..... 1. No enjoyment..... 2. Not very enjoyable..... 3. Fairly enjoyable..... 4. Highly enjoyable..... 5. Very enjoyable.....
 
9. When you had sexual stimulation or intercourse, how often did you ejaculate?
 
0. No sexual stimulation/intercourse  1. Almost never/never..... 2. A few time (much less than half the time)..... 3. Sometimes(about half the time).... 4. Most times (much more than half the time)..... 5. Almost always/always.....
 
10. When you had sexual stimulation or intercourse, how often did you have the feeling or orgasm or climax?
 
0. No sexual stimulation/intercourse..... 1. Almost never/never..... 2. A few time (much less than half the time)..... 3. Sometimes(about half the time).... 4. Most times (much more than half the time)..... 5. Almost always/always.....
 
11. How often have you felt sexual desire?
 
1. Almost never/never..... 2. A few times (much less than half the time)..... 3. Sometimes (about half the time). 4. Most times (much more than half the time)..... 5. Almost always/always.....
	
12. How would you rate your level of sexual desire?
 
1. Very low/none at all..... 2. Low..... 3. Moderate..... 4. High..... 5. Very high.....
 
13. How satisfied have you been with your overall sex life?
 
1. Very dissatisfied..... 2. Moderately dissatisfied..... 3. About equally satisfied and dissatisfied..... 4. Moderately satisfied..... 5. Very satisfied.....
 
14. How satisfied have you been with your sexual relationship with your partner?
 
1. Very dissatisfied..... 2. Moderately dissatisfied..... 3. About equally satisfied and dissatisfied..... 4. Moderately satisfied..... 5. Very satisfied.....
 
15. How do you rate your confidence that you could get and keep an erection?
 
1. Very low..... 2. Low..... 3. Moderate..... 4. High..... 5. Very high.....

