### ION04ED

If a patient has repeated assessments prior to the start of double-blind study drug, then the results from the final assessment made prior to the start of double-blind study drug will be used as baseline. If end-of-study assessments are repeated or unscheduled, the last post-baseline assessment will be used as the end-of-study assessment for generating summary statistics. However, all post-baseline assessments will be presented in the data listings.

Dose response comparisons will be made between 8000 mcg vs. 16000 mcg vs. placebo as well as comparisons between total active population (8000 mcg and 16000) vs. placebo. Onset and duration of effect will also be analyzed and a dose response evaluated. Onset and duration of action will also be analyzed.

All tests of significance with regard to efficacy will be one-tailed, and performed at an overall alpha level of .05. All estimates of differences will be presented with 95% confidence limits.

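### The Week 1 test of the IIEF erectile function score uses a one-month recall that falls mostly before the injection, so a between-group drug effect at that visit is diluted

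*SAP*

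**What the plan says.** Protocol Appendix D gives the IIEF with the recall period "In the last month". Protocol section 7.3 (Visit 3) lists "Participant completes the IIEF and SEP", and Appendix B places that visit at Week 1 ± 2 days. No shorter recall is given for it.

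The EF domain (items 1–5 and 15) is a primary outcome measure. SAP section 9.3 states: "The change in scores from baseline at each visit will be evaluated using one-sided paired t-test at 5% significance level". It adds that "a one-sided two sample t-test will be applied to compare the changes from baseline in scores between the two treatment groups", followed by a repeated-measures ANOVA for the effect of visit. SAP section 6 takes baseline as the last value before treatment, which is Visit 2.

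The protocol agrees. The Synopsis says EF change "at every visit after administration of study drug will be calculated and compared among the two dose and one placebo groups". Section 10.3.2 twice calls for evaluation at all visits, the second time as "questions will be evaluated at all visits and changes compared to baseline and placebo using either paired t-tests for normally distributed changes".

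SAP section 9 adds: "Onset and duration of effect will also be analyzed and a dose response evaluated". It names no endpoint for onset. SAP section 7 uses LOCF without limiting which score may be carried. Neither document mentions the overlap between the recall period and the time before dosing.

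**The concern.** At Week 1 a man has had 5 to 9 days since injection but is asked about a month. Most of the days he is asked about came before treatment, and those same days lie inside the recall window of his Visit 2 baseline. To that extent, the Week 1 change compares the baseline period with itself.

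Three readings of the data are at stake:

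- A null between-group EF result at Week 1 could be taken as absence of early activity when the instrument could hardly have shown it.
- The effect of visit in the repeated-measures analysis could show EF climbing from Week 1 to Week 4 even if the drug effect were constant from day 0.
- Onset, if judged on EF, would appear later than it was.

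A Week 1 score can also stand in for later visits through LOCF.

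**Working it through.** **Plan's own figure.** The documents give no figure for the overlap. The nearest is the power table (Protocol Table 2; SAP section 8): means 10.0 and 6.6, SD 2.5, alpha 0.0167, 80% power, ratio 1.111. The two-sided normal formula gives (3.235)² × (2.5/3.4)² × (1 + 1/1.111) = 10.75, so 11; and 11 × 1.111 = 12.2, so 13. This matches the stated 11 and 13. The table names no endpoint or visit, so its 3.4 points (10.0 − 6.6) serve below only as an illustration.

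**Calendar share before injection.** Inputs: visit day d from Appendix B; month length M = 28 to 31 days (assumed, because the form gives no day count). Share = (M − d)/M, or 0 if d ≥ M.

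| Visit | Days | Lowest | Highest |
|---|---|---|---|
| Week 1 | 5–9 | (28 − 9)/28 = 68% | (31 − 5)/31 = 84% |
| Week 4 | 25–31 | 0% | (31 − 25)/31 = 19% |
| Week 8 | 53–59 | 0% | 0% |

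At day 7 of 28 the share is 21/28 = 75%.

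**Illustrative dilution of 3.4 points at Week 1.** Assume the full effect from day 0, and let f be the post-dose share, 5/31 = 0.161 to 9/28 = 0.321.

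- Equal weight per day: 3.4f = 0.55 to 1.09.
- Post-dose days counted double: 3.4 × 2f/(1 + f) = 0.94 to 1.65.
- Item 15 ("How do you rate your confidence that you could get and keep an erection") answered as a current rating and carrying one-sixth of the effect: 3.4 × (5f + 1)/6 = 1.02 to 1.48.

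**Apparent rise over visits.** With equal weighting, the same constant effect would read 0.55–1.09 at Week 1 and 3.4 × 25/31 = 2.74 to 3.4 at Week 4.

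**Power at Week 1.** The overlap may also shrink the SD of change. Let e be the share of variance that is reporting error, so SD = 2.5 × √(e + (1 − e)f²). Take f = 0.25, a difference of 0.85, 11 versus 13, one-sided 0.05, noncentral t:

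| e | SD | Power |
|---|---|---|
| 1 | 2.50 | 20% |
| 0.5 | 1.82 | 29% |
| 0.25 | 1.36 | 43% |
| 0 | 0.62 | 94% |

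Undiluted power is 94%. The documents do not give e, so the loss of power cannot be determined.

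**One man carrying Week 1 forward by LOCF.**

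- Active arm, 1 of 11, diluting only the treatment difference: 3.4 × (10 + f)/11 = 3.14 to 3.19.
- Active arm, reading the table means as changes and diluting the whole change: 10.0 × (10 + f)/11 = 9.24 to 9.38, so the difference falls to 2.64–2.78.
- Placebo arm, 1 of 13, on that second reading: 6.6 × (12 + f)/13 = 6.17 to 6.26, so the difference rises to 3.74–3.83.

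**The case against.** The best case against acting is that the harm is narrow. Week 1 is one of five post-dose visits and neither document makes it decisive. Overlap is slight at Week 4 and absent from Week 8. A low Week 1 value does not bias the later visit means. The onset harm arises only if EF is used. SEP2 and SEP3, also primary measures, are recorded attempt by attempt and tested at each post-dose visit. All of this stands, and it limits the severity.

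Four stronger readings are tempting, but the documents do not support them:

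- **That 68–84% of the effect is lost, or that this is an upper bound.** It is a share of calendar days. Recent attempts may weigh more and item 15 may reflect the present, which reduces dilution. A man with no attempt since injection answers items 1–5 wholly from pre-dose experience, which takes the share above 84%.
- **That the bias is always conservative.** LOCF applies to every arm, and Protocol section 8.0 lets men leave for perceived lack of effect. A placebo man carrying a diluted placebo response widens the later difference.
- **That within-group change at Week 1 must be attenuated.** The undertaking to attempt intercourse four times a month applies while in the study, and screening is at Week −2. On a 28-day month, the Visit 2 window holds about 14 on-study days and the day 7 window about 21. Items 1–5 score 0 for no activity or attempt, so scores can rise without any drug effect. Placebo response and regression to the mean can also move them.
- **That the Week 1 test is shown to be underpowered.** The range runs from 20% to 94%, and the upper end is no loss at all.

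**Conclusion.** The concern holds for the treatment-caused between-group EF difference at Week 1, for the step from Week 1 to Week 4 in the repeated-measures analysis, and for any EF-based onset estimate. The recall overlap of 68–84% at Week 1 follows from the form and the visit window, given a 28 to 31 day month. The size of the dilution is less certain: under the three weightings tried, an immediate 3.4-point effect would show as 0.5 to 1.7 points, so at least half would be hidden.

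LOCF of a Week 1 score shifts later comparisons by less than 0.8 points per man carried, in a direction that depends on which arm loses men. The efficacy conclusions from Week 4 on are largely untouched. Severity is minor to moderate.

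**What to change.** Protocol section 10.3 says the final SAP will be issued before the code is broken. Before then:

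1. In SAP section 9.3, make Visit 4 (Week 4) the first post-dose EF visit for hypothesis tests and for the repeated-measures analysis. Report Week 1 EF descriptively, with the recall overlap stated. Align the Synopsis sentence and, for the IIEF only, the two sentences in Protocol section 10.3.2.
2. If early onset is analysed, base it on the dated SEP2 and SEP3 diary attempts (Appendix C). State that they are sparse: at four attempts a month, about one per man in Week 1.
3. Keep the planned LOCF analysis. Add a sensitivity analysis that does not carry forward an EF score taken before the Visit 4 window opens (day 25), and report by arm how many men are affected. Dropping these scores from the main analysis is not advised, because it would exchange a limited shift for selection among men with later data.

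Cost: SAP wording, three protocol sentences, one fewer inferential EF time point and one extra sensitivity analysis. Visits, data collection and analysis sets do not change.
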